## **10.7 Justification of Surrogate Consent**

According to the Belmont Report, respect for persons incorporates at least two ethical convictions; first, that individuals should be treated as autonomous agents, and second, that persons with diminished autonomy are entitled to protection. One method that serves to protect patients is restrictions on the participation of patients in research that presents greater than minimal risk. Commentators and research ethics commissions have held the view that it is permissible to include incapable participants in greater than minimal risk research as long as there is the potential for beneficial effects and that the research presents a balance of risks and expected direct benefits similar to that available in the clinical setting. Several U.S. task forces have deemed it permissible to include incapable participants in research. For example, the American College of Physicians' document allows surrogates to consent to research involving incapable participants only "if the net additional risks of participation are not substantially greater than the risks of standard treatment". Finally, NBAC stated that an IRB may approve a protocol that presents greater than minimal risk but offers the prospect of direct medical benefits to the participant, provided that "the potential subject's LAR gives permission...".

Consistent with the above ethical sensibilities regarding the participation of decisionally incapable participant in research and the previous assessment of risks and benefits in the previous section, the present trial presents a balance of risks and potential direct benefits that is similar to that available in the clinical setting.

## **10.8 Additional Safeguards for Vulnerable Participants**

The present research will involve participants who might be vulnerable to coercion or undue influence. As required in 45CFR46.111(b), we recommend that sites utilize additional safeguards to protect the rights and welfare of these participants. Such safeguards might include but are not limited to: a) assessment of the potential participant's capacity to provide informed consent, and b) the availability of the LAR to monitor the participant's subsequent participation and withdrawal from the study. The specific nature of the additional safeguards will be left to the discretion of the central IRB, in conjunction with the sites.

## **10.9 Confidentiality**

Federal regulations at 45 CFR 46 111 (a) (7) requires that when appropriate, there are adequate provisions to protect the privacy of participants and to maintain the confidentiality of data. At no time during the course of this study, its analysis, or its publication will patient identities be revealed in any manner. The minimum necessary data containing patient or provider identities will be collected. All patients will be assigned a unique study ID number for tracking. All data collected for this study will be entered directly into a secure online database. All data will be maintained in the secure online database until the time of study publication. At the time of publication, a de-identified version of the database will be generated. Further, tools within the secure online database will be used so that only the coordinating center and investigators from the enrolling site will have access to data from participants enrolled at that site.

# **11. ADVERSE EVENTS**

Assuring patient safety is an essential component of this protocol. Magnesium citrate has been approved by the Food and Drug Administration and used in clinical practice for decades with an established safety profile. Use of magnesium citrate plus the probiotic Floranex for the treatment of acute respiratory infection due to COVID-19, however, raises unique safety considerations. This protocol addresses these considerations through:

1. Exclusion criteria designed to prevent enrollment of patients likely to experience adverse events with receipt of magnesium citrate or the probiotic Floranex, such as those with creatinine clearance of <30cc/min;
2. Proactive education of treating clinicians regarding medication interactions relevant to use of magnesium citrate plus the probiotic Floranex in the inpatient setting;
3. On-study monitoring of co-interventions (e.g., medications) and patient characteristics (e.g., EKG) to intervene before adverse events occur;
4. Systematic collection of safety outcomes relevant to use of magnesium citrate plus the probiotic Floranex in this setting;
5. Structured reporting of adverse events

### **11.1 Adverse Event Definitions**

**Adverse Event:** Any untoward medical occurrence associated with the use of a drug or a study procedure, whether or not considered drug related.

**Serious Adverse Event:** A serious adverse event is any adverse event that results in one of the outcomes listed in section 11.3 below.

**Adverse Reaction:** An adverse reaction means any adverse event caused by a study intervention. An adverse reaction is a subset of all suspected adverse events where there is a reason to conclude that the study intervention caused the event.

**Suspected Adverse Reaction:** Any adverse event for which there is a reasonable possibility that the study procedures caused the adverse event. Reasonable possibility means there is evidence to suggest a causal

relationship between the study procedures and the adverse event. A suspected adverse reaction implies a lesser degree of certainty about causality than adverse reaction.

**Suspected Unexpected Serious Adverse Reaction (SUSAR):** An adverse reaction that is both unexpected (not consistent with risks outlined in the study protocol or investigator brochure), serious, and meets the definition of a suspected adverse reaction.

## 11.2 Safety Monitoring

Assuring patient safety is an essential component of this protocol. Each participating investigator has primary responsibility for the safety of the individual participants under his or her care. The Investigators will determine daily if any adverse events occur during the period from enrollment through **study day 7** or hospital discharge, whichever occurs first and will determine if such adverse events are reportable. Thereafter, adverse events are not required to be reported unless the investigator feels the adverse event was related to study drug or study procedures.

The following adverse events will be considered reportable and thus collected in the adverse event case report forms:

- Serious adverse events
- Non-serious adverse events that are considered by the investigator to be related to study procedures or of uncertain relationship (Appendix C)
- Events leading to permanent discontinuation of study drug

Study-specific clinical outcomes (Primary, Secondary and Safety Outcomes and Assessments During the Study), including serious outcomes such as organ failures and death, are systematically recorded in the case report forms and are exempt from adverse event reporting unless the investigator deems the event to be related to the administration of study drug or the conduct of study procedures (or of uncertain relationship) as outlined in Appendix C.

After randomization, adverse events must be evaluated by the investigator. If the adverse event is judged to be reportable, as outlined above, then the investigator will report to the Clinical Coordinating Center (CCC) their assessment of the potential relatedness of each adverse event to the study drug or protocol procedure via electronic data entry. Investigators will assess if there is a reasonable possibility that the study procedure caused the event, based on the criteria outlined in Appendix C. Investigators will also consider if the event is unexpected. Unexpected adverse events are events not listed in the study protocol and the package insert for the study drugs will also determine if adverse events are unanticipated given the patient's clinical course, previous medical conditions, and concomitant medications.

If a patient's treatment is discontinued as a result of an adverse event, study site personnel must also report the circumstances and data leading to discontinuation of treatment in the adverse event case report forms.

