## **6.3 Assessments following Hospital Discharge**

### **6.3.1 Acute Care Follow-up**

For participants discharged from the study hospital prior to the Day 7 or Day 29 assessment, we will perform these assessments via telephone follow-up. The Day 7 call window will be Day 7 through day 14. The Day 29 call window will be Day 29 through day 36. During these telephone calls, we will interview the patient, LAR, or facility staff to assess:

- Date of death (if applicable)
- ED visits, hospital readmissions, and use of supplemental oxygen after hospital discharge
- Non-laboratory safety outcomes after hospital discharge and adverse events
- Symptoms of acute respiratory infection
- COVID Ordinal Outcomes Scale

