## 11.3 Serious Adverse Events

Serious adverse event collection begins after randomization and study procedures have been initiated. If a patient experiences a serious adverse event after consent, but prior to randomization or starting study procedures, the event will NOT be collected. Study site personnel must alert the CCC of any **serious and study procedure related** adverse event within 24 hours of investigator awareness of the event. Alerts issued via telephone are to be immediately followed with official notification on the adverse event case report form. See Appendix C for reporting timelines for serious, unexpected, study related events (SAEs) and serious, unexpected suspected adverse reactions (SUSARs)

As per the FDA and NIH definitions, a serious adverse event is any adverse event that results in one of the following outcomes:

- Death
- A life-threatening experience (that is, immediate risk of dying)
- Prolonged inpatient hospitalization or re-hospitalization

As per <http://www.fda.gov/Safety/MedWatch/HowToReport/ucm053087.htm>: Report if admission to the hospital or prolongation of hospitalization was a result of the adverse event. Emergency room visits that do not result in admission to the hospital should be evaluated for one of the other serious outcomes (e.g., life-threatening; required intervention to prevent permanent impairment or damage; other serious medically important event).

- Persistent or significant disability/incapacity

As per <http://www.fda.gov/Safety/MedWatch/HowToReport/ucm053087.htm>: Report if the adverse event resulted in a substantial disruption of a person's ability to conduct normal life functions, i.e., the adverse event resulted in a significant, persistent or permanent change, impairment, damage or disruption in the patient's body function/structure, physical activities and/or quality of life.

Reportable serious adverse events that may not result in death, be life-threatening, or require hospitalization may be considered serious adverse events when, based upon appropriate medical judgment, they may jeopardize the patient and may require medical or surgical intervention to prevent one of the outcomes listed in this definition. Serious adverse events will be collected until hospital discharge, regardless of the investigator's opinion of causation.

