## APPENDICES

### Appendix A. Schedule of Events

Study Activity	Pre-enrollment	Day 1	Day 2	Day 3	Day 4	Day 5	Day 6	Day 7	Day 8 through Discharge	Day 29	Acute Care F/U (by phone if discharged prior to Day 7 or Day 29)	3 Mos. F/U
Eligibility assessment	X											
Pregnancy test (if applicable)	X											
Informed consent	X											
COVID Ordinal Outcome Score Assessment 	X		X	X	X	X	X	X	X	X	X	
Randomization		X										
Baseline Variable Data Collection		X										
Blood Sample Collection		X						X				
Nasal Swab Collection		X		X						X		
Sequential Organ Failure Assessment (SOFA)		X		X								
ARDS Evaluation 		X	X	X	X	X	X	X	X	X		
Study Drug Delivery		X										
Study Variable Data Collection 			X	X	X	X	X	X	X	X		
Assessment of Study Drug Adherence 		X	X	X	X	X	X					
Adverse Events Monitoring/Assessment		X	X	X	X	X	X	X		X	X	
Safety Outcomes Assessment		X	X	X	X	X	X	X	X	X		
Mortality Assessment								X		X	X	
Long-term Outcomes 												X

Assessed if patient remains hospitalized; assessed by telephone follow-up if participant has been discharged

Assessed in-person, by telephone or videophone.

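### Sections 11.2, 11.3, 6.3.1 and Appendix A disagree on how long events not judged related are collected, and two of the windows can close at discharge, which is a secondary outcome

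*Combined protocol and SAP*

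**What the plan says.** Four places in the combined protocol and SAP govern the collection of adverse events.

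- **Section 11.2.** Investigators check daily from enrollment to Study Day 7 "or hospital discharge, whichever occurs first and will determine if such adverse events are reportable". The section then says: "Thereafter, adverse events are not required to be reported unless the investigator feels the adverse event was related" to study drug or procedures. Its list of reportable events has three items: SAEs; non-serious events judged related or of uncertain relationship; and events that lead to study drug being stopped for good. SAEs get no exception from the cut-off.
- **Section 11.3.** "Serious adverse events will be collected until hospital discharge, regardless of the investigator's opinion of causation". There is no Day 7 limit. One of the SAE criteria is "Prolonged inpatient hospitalization or re-hospitalization".
- **Appendix A.** The row "Adverse Events Monitoring/Assessment" is marked on Days 1 to 7, blank in the Day 8 through Discharge column, and marked again at Day 29 and at the acute care phone follow-up.
- **Section 6.3.1.** For patients already discharged, the Day 7 and Day 29 calls cover "Non-laboratory safety outcomes after hospital discharge and adverse events", as well as readmissions. No relatedness condition is attached. The Day 29 call may be made up to Day 36.

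Section 5.2 lists time to discharge and hospital-free days as secondary outcomes, and discharge is also a component of time to recovery.

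**The concern.** There are two problems. First, site staff following these sections cannot tell whether some serious events have to be recorded, so two coordinators could handle the same event differently and both be following the protocol.

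Second, the windows in 11.2 and 11.3 can close at discharge, which treatment is meant to bring forward. If one arm goes home sooner, its patients are watched for fewer days, and a lower count of unrelated SAEs would follow even with identical underlying rates. Once the window has closed, an event enters the record as reportable only if the investigator judges it related. Section 2.1 names safety as something the trial will evaluate, and Section 12 and Appendix C have the DSMB review reported adverse events at interim analyses. Unequal collection could therefore reach those reviews.

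**Working it through.** The plan gives no figure to reproduce, so the check sets the sections side by side.

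**Step 1. Follow specific events through each section.** Assume each event is outside the exempt list in Appendix C.3 and, except in the last row, is judged unrelated.

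| Event | 11.2 | 11.3 | Appendix A, AE row | 6.3.1 calls |
|---|---|---|---|---|
| SAE, Day 5, in hospital | required | required | marked | not applicable |
| SAE, Day 10, still in hospital | not required | required | blank | not applicable |
| SAE after discharge, e.g. readmission | not required | not required | marked at phone follow-up and Day 29 | asked |
| Non-serious event after discharge | not required | not covered | marked at phone follow-up and Day 29 | asked |
| Event judged related, any time | reportable | SAEs to discharge | as above | asked |

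The second and third rows carry the point. The Day 10 inpatient SAE gets a different answer from 11.2 and 11.3. The readmission meets an SAE criterion but follows discharge, when 11.3 collection has stopped. A call will ask about it, yet neither 11.2 nor 11.3 requires it as an SAE unless it is judged related.

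**Step 2. Narrow down what is affected.** Non-serious unrelated events are on the 11.2 list only if they lead to study drug being stopped for good. Section 4.2 gives capsules for at most six days and not beyond discharge, so few if any such events can fall after the window. Related events have no cut-off in 11.2. Deaths, organ failures and the other outcomes in Appendix C.3 go into the case report forms separately. What remains is mainly unrelated SAEs outside that list.

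**Step 3. Window length by day of discharge.** For an event not judged related and a patient discharged on day d, the window is min(d, 7) days under 11.2 and d days under 11.3 (SAEs only). The Appendix A and 6.3.1 contacts reach Day 29.

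| d | 11.2 | 11.3 | Last scheduled contact | Days from discharge to Day 29 |
|---|---|---|---|---|
| 5 | 5 | 5 | Day 29 | 29 − 5 = 24 |
| 10 | 7 | 10 | Day 29 | 29 − 10 = 19 |
| 15 | 7 | 15 | Day 29 | 29 − 15 = 14 |

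Under 11.2 the window depends on discharge only in patients who leave before Day 7. Under 11.3 it depends on discharge for any stay.

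**Step 4. Direction of the effect, with assumed inputs.** Take the same daily event rate r in both arms, constant in and out of hospital, so that P(at least one event) = 1 − exp(−r × window). Neither r nor the discharge days come from the documents.

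- Discharge on Day 4 against Day 6, under 11.2 or 11.3: 0.077/0.113 = 0.68 at r = 0.02 per day; 0.181/0.259 = 0.70 at r = 0.05.
- Day 5 against Day 7, under 11.2 or 11.3: 0.095/0.131 = 0.73; 0.221/0.295 = 0.75.
- Day 5 against Day 10 under 11.2: the later discharge is capped at Day 7, so again 0.73 and 0.75.
- Day 5 against Day 10 under 11.3: 0.095/0.181 = 0.52; 0.221/0.393 = 0.56.
- Any pair with a fixed window to Day 29: 1.00.

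These ratios show that a window ending at discharge favours the arm discharged earlier and that a common window removes the effect. They do not estimate what would happen in this trial.

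**The case against.** The strongest defence is that the sections are tiered. On that reading, 11.2 sets the general rule, 11.3 is the specific rule for serious events and extends it to discharge, the blank Appendix A cell follows the Day 7 limit in 11.2, and the calls are how late related events come to light. Part of this stands: asking about adverse events on a call is compatible with requiring reports only of related ones. But tiering does not settle the Day 10 case, because 11.2 includes SAEs in its own list and exempts none from the cut-off, and Appendix A schedules no assessment in the period where 11.3 needs one. Appendix C does not settle it either, since its 24-hour rule concerns events with possible or uncertain relatedness.

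It is also fair to say that follow-up is wider than 11.2 suggests. Appendix A schedules safety outcomes and mortality to Day 29, and the calls ask about deaths, emergency visits and readmissions. This limits the harm considerably, although 6.3.1 restricts safety outcomes after discharge to non-laboratory ones. Section 7 specifies no between-arm comparison of adverse event rates, so no planned test is biased; what is exposed is the DSMB's review and any safety table by arm. Finally, planned exposure is over by Day 7. That could justify a shorter window, but not one that varies with discharge.

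Three stronger readings are tempting, and the documents do not support them:

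- A reader might infer that adverse event collection ends on three different dates. It does not: related events stay reportable under 11.2 with no end date, and Day 29 is an assessment point, not a stated end of collection.
- A reader might infer a definite shortfall of adverse events in the arm discharged earlier. That needs lengths of stay and event rates that the plan does not give, and it would apply only to the narrow class left after Step 2.
- A reader might use the 60.8% discharged in Table 1 to count patients lost to the window. That is Day 15 status in a different trial, of patients early in critical illness; under 11.2 every patient has left routine collection by Day 7 anyway.

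**Conclusion.** The inconsistency is real and limited. For events not judged related, the four places give incompatible instructions in two situations: an SAE after Day 7 in a patient still in hospital, and any event after discharge. The practical gap is mainly unrelated SAEs outside the exempt list, including readmissions not judged related.

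The dependence on discharge is also real for 11.2 and 11.3, so observation time for these events can differ between arms. That it would favour the arm discharged earlier rests on comparable event rates in the two arms and on a difference in discharge timing. Its size cannot be derived from the documents. This is a cheap improvement worth making, not a flaw that undermines the trial.

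**What to change.** Reconcile 11.2, 11.3, 6.3.1 and Appendix A to one stated window per event type:

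- Collect SAEs, whatever the causal judgement, from the first study procedure to Day 29 in every randomized patient, whether in hospital or at home.
- State the window for non-serious reportable events once, and refer to it from the other sections.
- Fill the Day 8 through Discharge cell in the Appendix A adverse event row.
- Take events after discharge, including readmissions, from the Day 7 and Day 29 calls already scheduled, and record those that meet an SAE criterion as SAEs.
- Compare the arms over that common window, for the DSMB and in the final report.

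The cost is protocol wording and modest extra data entry. No new patient contacts are needed.

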## 2. TRIAL DESCRIPTION

### 2.1 Background

Coronavirus Disease 2019 (COVID-19) is an acute respiratory infectious illness caused by *severe acute respiratory syndrome coronavirus 2* (SARS-CoV-2). Although the epidemiology has not been fully elucidated, most adults with COVID-19 appear to experience fever, cough, and fatigue and then recover within 1-3 weeks. However, a portion of adults with COVID-19 develop severe illness, typically manifesting as pneumonia and hypoxic respiratory failure, with continued progression to acute respiratory distress syndrome (ARDS) and death in some cases. The incidence and mortality of COVID-19 cases continues to climb in the United States, as well as around the world. While progress for vaccination and identifying therapeutics against SARS-CoV-2 have emerged, the limitations continue to emerge. For example, convalescent plasma was recently demonstrated to hold little promise against COVID-19 severe pneumonia[1]. While remdesivir demonstrates efficacy in hospitalized COVID-19 patients with pneumonia[2], the NIH no longer recommends remdesivir with dexamethasone as an option for hospitalized COVID-19 patients who require mechanical ventilation or ECMO, recommending only dexamethasone instead (COVID-19 Treatment Guidelines Panel. Coronavirus Disease 2019 (COVID-19) Treatment Guidelines. National Institutes of Health. Available at <https://www.covid19treatmentguidelines.nih.gov/>. Accessed 12/07/2020). Thus, data on the safety and effectiveness of magnesium citrate plus the probiotic Floranex for the treatment of COVID-19 are urgently needed to inform clinical practice. In this trial, we will evaluate the safety and effectiveness of magnesium citrate plus the probiotic Floranex for the treatment of adults hospitalized with COVID-19.

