#### **9.1.1 Potential risks of receiving magnesium citrate**

Common Side effects of magnesium citrate include:

Abdominal cramping

Diarrhea

Electrolyte imbalance

Gas (flatulence)

Nausea

Vomiting

Hypermagnesemia (high levels of magnesium in the blood).

Side effects that can occur with Hypermagnesemia:

Nervous system

- Muscle weakness, decrease in tendon reflexes, mental confusion, or sedation when serum magnesium (Mg) levels increase to 4 to 7 mEq/L,
- Slowed respiratory rate and hypotension when serum magnesium (Mg) levels increase to 5 to 10 mEq/L

- Profound mental depression, areflexia, coma and respiratory paralysis when serum Mg levels increase to 10 to 15 mEq/L
- Death possible when serum Mg levels rise to 15 mEq/L or higher.

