### C.2. Determining Relationship of Adverse Events to Study Drug or Study Procedures

Investigators will be asked to grade the strength of the relationship of an adverse event to study drug or study procedures as follows:

- Definitely Related: The event follows: a) A reasonable, temporal sequence from a study procedure; and b) Cannot be explained by the known characteristics of the patient’s clinical state or other therapies; and c) Evaluation of the patient’s clinical state indicates to the investigator that the experience is definitely related to study procedures.
- Probably or Possibly Related: The event should be assessed following the same criteria for “Definitely Associated”. If in the investigator’s opinion at least one or more of the criteria are not present, then “probably” or “possibly” associated should be selected.

- Probably Not Related: The event occurred while the patient was on the study but can reasonably be explained by the known characteristics of the patient's clinical state or other therapies.
- Definitely Not Related: The event is definitely produced by the patient's clinical state or by other modes of therapy administered to the patient.
- Uncertain Relationship: The event does not meet any of the criteria previously outlined.

[figure not shown]

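### Non-serious adverse events that are not named outcomes and do not permanently stop the study drug are recorded only if judged related or uncertain, so their counts by arm would partly reflect attribution

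*Combined protocol and SAP*

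**What the plan says.** Section 2.1 states that "we will evaluate the safety and effectiveness of magnesium citrate plus the probiotic Floranex". Section 11.2 then sets what is recorded: "The following adverse events will be considered reportable and thus collected in the adverse event case report forms". Three classes follow:

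- serious adverse events, which 11.3 gathers without regard to cause: "Serious adverse events will be collected until hospital discharge, regardless of the investigator's opinion of causation";
- a class that turns on the investigator's opinion: "Non-serious adverse events that are considered by the investigator to be related to study procedures or of uncertain relationship (Appendix C";
- a last class, with no condition on cause: "Events leading to permanent discontinuation of study drug".

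Named study outcomes go by a separate route. They "are systematically recorded in the case report forms and are exempt from adverse event reporting unless the investigator deems the event to be related"; an uncertain relationship also ends the exemption. These are the four safety outcomes in 5.3, the eight checked daily under 6.2, and the examples in C.3.

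Section 9.1.1 lists the common effects of magnesium citrate: cramping, diarrhea, electrolyte imbalance, gas, nausea, vomiting and hypermagnesemia. For raised magnesium it adds, among others, "Muscle weakness, decrease in tendon reflexes, mental confusion, or sedation when serum magnesium (Mg) levels increase to 4 to 7 mEq/L". Section 9.1.2 lists gas, bloating and diarrhea for Floranex.

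C.2 gives the grade *Probably Not Related* to an event for which the illness or another treatment accounts (its wording begins "can reasonably be explained by the known characteristics of the").

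**The concern.** Relatedness normally decides how fast an event is reported. Here, for one class of events, it decides whether the event is recorded at all. Section 11.1 defines an adverse event without regard to cause, so the collection rule in 11.2 is narrower than the protocol's own definition.

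Randomization lets causality be judged by comparing arms. A filter applied patient by patient removes events before they can be compared, and it most readily removes those the illness could also explain. Nausea, vomiting, weakness, confusion or sedation in a COVID-19 inpatient could each be put down to the disease. The introduction to Section 11 promises systematic collection of safety outcomes relevant to these products, yet their commonest listed effects are not on the systematic lists. Events that were never recorded cannot be recovered at analysis.

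**Working it through.** **1. Which events pass through the filter**

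| Event class | Recorded | Depends on judged cause? |
|---|---|---|
| Serious events (11.2, 11.3) | Adverse event form | No |
| Events that permanently stop the drug (11.2) | Adverse event form | No |
| Named outcomes (5.3, 6.2, C.3): e.g. dehydration, hypotension, kidney injury, arrhythmia, pancreatitis | Case report form, all patients | No |
| Other non-serious events | Adverse event form | Yes |

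None of the common effects in 9.1.1, and none of those in 9.1.2, appears in 5.3, 6.2 or C.3. The same holds for weakness, confusion and sedation. When non-serious, all of these fall in the last row. The discontinuation route helps little with magnesium citrate: 4.2 gives it once, with a possible second bottle, so an effect that follows the dose can mostly stop only the six-day capsules.

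**2. How C.2 sorts an event that the illness could explain**

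- *Definitely Related* needs three criteria. Criterion (b) is that the clinical state or other therapies cannot explain the event. This event fails (b).
- *Probably or Possibly Related* applies when one or more of those criteria are absent. The event fits, and would be reportable.
- *Probably Not Related* applies when the clinical state reasonably explains the event. The event fits here too, and would not be reportable if non-serious.
- *Uncertain Relationship* is for events meeting none of the other criteria, so this event does not clearly belong there.

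The same event can therefore be recorded or not, depending on which line the investigator applies.

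**3. Illustration of size**

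The documents give no adverse event rates and no power for harms, so there is no plan figure to reproduce. The number per arm is 15 (Section 7.1). The rates below are assumptions: true incidence 40% on active and 20% on placebo, with a share *q* of events judged reportable, equal in both arms.

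Recorded counts are X ~ Binomial(15, 0.40*q*) and Y ~ Binomial(15, 0.20*q*). The quantity is P(X − Y ≥ 3), summed exactly over all pairs of counts. Three is the expected excess with full recording: 15 × (0.40 − 0.20) = 3.

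| *q* | Recorded rates | Expected counts | P(X − Y ≥ 3) |
|---|---|---|---|
| 100% | 40% vs 20% | 6.0 vs 3.0 | 0.584 |
| 80% | 32% vs 16% | 4.8 vs 2.4 | 0.483 |
| 50% | 20% vs 10% | 3.0 vs 1.5 | 0.297 |
| 20% | 8% vs 4% | 1.2 vs 0.6 | 0.071 |

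With equal capture the risk ratio stays at 2. The risk difference shrinks in proportion to *q*, from 20 points to 16, 10 and 4.

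**The case against.** Much of the harms data escapes the filter. Serious events, permanent discontinuations and named outcomes are recorded whatever the cause, and several effects that could be confused with severe illness are among those outcomes. Under 4.6, even a temporary stop leaves its reason on the case report form. Appendix C has the DSMB review clinical outcomes as well as reported events. All of this stands and limits the point to the last row of the table above.

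Events of uncertain relationship are collected, and an investigator could well grade vomiting soon after a 296 mL oral dose as possibly related. That is fair, and is why such effects *may* be missed rather than will be. It does not repair C.2, which supports either grade. Exclusion 9 in Section 3 removes patients with creatinine clearance below 30 mL/min, which makes the high-magnesium effects less likely but leaves the common effects untouched.

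Targeted collection also fits Section 6's aim of limiting research activity. The saving is small in about 30 patients whom 11.2 already has assessed daily.

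Two stronger readings are tempting. One is that the trial's whole comparison of harms is distorted. The exceptions above contradict this, and Section 7 prespecifies no comparison of harms by arm. The other is that the filter favors one arm. Investigators are blinded (2.3, 3.7) and the placebo is flavor-matched, so unequal attribution is not established. Bowel effects might reveal the arm, since a laxative is compared with lemon water, but that is an inference. If capture were 60% vs 30% with equal true rates of 40%, the chance of a spurious excess of three or more would rise from 0.176 to 0.365; nothing in the documents supports those shares.

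**Conclusion.** The point holds for non-serious events that are neither named outcomes nor causes of permanent discontinuation. That class contains the common effects the protocol lists for both products. Counts of these events by arm would partly reflect attribution, and effects resembling COVID-19 may go unrecorded. The overlap in C.2 makes recording depend further on the individual investigator.

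The size is illustrative. With 15 per arm and assumed true rates of 40% vs 20%, the chance of an excess of three or more falls from 58% to between 48% and 7% as equal capture falls from 80% to 20%. The threshold of three is not a protocol criterion, and the actual capture share is unknown. The direction does not depend on these choices when capture is equal: incomplete recording shrinks the recorded difference. The remedy is a cheap improvement to a trial that states a safety aim.

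**What to change.** In 11.2, replace the non-serious bullet with: *all non-serious adverse events that begin or worsen from randomization to Study Day 7 or hospital discharge, whichever is first, whatever their judged relationship*. Keep the existing exemption for study-specific outcomes recorded elsewhere. This stays within the present daily assessment window and leaves the post-discharge rule unchanged.

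At minimum, add the effects in 9.1.1 and 9.1.2 to the daily safety outcomes in 6.2 for all patients, using laboratory values available from clinical care.

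Under either option:

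- keep relatedness as a recorded field and as the trigger for expedited reporting only;
- word it throughout as relatedness to study drug or study procedures, since the present bullet names procedures alone;
- tabulate all events by randomized arm first, and related events second;
- redefine the C.2 grades so that an event explained by the clinical state fits only one.

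The cost is more form entries for about 30 patients over at most 7 days, plus a short edit to C.2 and one table added to the analysis plan.
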